#### **9.4.2 Primary endpoint(s)**

The primary endpoint is the time to improvement of 2 points in clinical status assessment from baseline using the 7-point ordinal scale. Patient who discharged early will be considered as meeting the two points improvement criteria.

The primary endpoint will be analyzed using a log-rank test stratified by randomization stratum with treatment as a fixed factor in the mITT population. P-value for the pairwise treatment comparison versus placebo will be provided. Estimation of treatment effect of each sarilumab dose will be provided as hazard ratio (sarilumab versus placebo) using Cox proportional hazards model stratified by the randomization stratum with treatment as a covariate, along with 2-sided confidence intervals. Kaplan-Meier (KM) plot and the median time-to- improvement of 2 points will also be provided.

Superiority of sarilumab over placebo will be declared if the null hypothesis is rejected at the 5% (2-sided) significance level following the multiplicity control procedure specified in [Section 9.4.3.1](#).

Patients who have an improvement of 2-points in clinical assessment or discharge will be considered as events, while patients who do not experience improvement of 2-points will be censored at the last observation time point. Patients who die or take rescue medication in the study without improvement of 2-points before that will be censored at the earlier date of Day 29 (for the primary analysis) or rescue medication started.

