Patients who achieved resolution of fever or discharge (other than death) will be considered as events, while patients who do not experience resolution of fever will be censored at the end of study. Patients who started rescue therapy or died in the study will not be considered as having an endpoint event and will be censored at the earlier date of death or rescue therapy start date. Patients who do not have fever at baseline will be censored at the first dose date.

Analysis of endpoint #5: the number of days with fever

Fever is defined as body temperature $>37.4^{\circ}\text{C}$ (axillary), or $>38^{\circ}\text{C}$ (oral), or $>38.4^{\circ}\text{C}$ (rectal or auricular).

The number of days with fever will be analyzed using the ANCOVA model with treatment group and randomization strata as fixed effects for patients alive by Day 29. The LS treatment mean difference from placebo with standard error, along with corresponding 95 % confidence interval and p-value will be provided.

Summary statistics with mean, median, standard deviation, minimum and maximum will be provided. Histogram will be provided to illustrate the distribution of days with fever.

In addition, the percent of days with fever ($100 \times$ number of days with fever divided by number of days of follow-up, defined as the earlier date of death or discharge or last visit up to Day 29) for all patients, will be analyzed using the ANCOVA model with treatment group and randomization strata as fixed effects.

Improvement in Oxygenation

Improvement in oxygenation is defined as increasing in SpO₂/FiO₂ of 50 or greater compared to the nadir SpO₂/FiO₂. Nadir SpO₂/FiO₂ is the nadir (lowest value) at any point in the study, and looking forward, an improvement in oxygenation is increase of 50 or greater from nadir value for at least 48 hours. If nadir is observed on 2 or more different days post baseline, the day of the first occurrence of nadir will be used.

Baseline SpO₂/FiO₂ ratio is defined as the last available ratio prior to first dose.

Post-Baseline SpO₂/FiO₂ ratio is defined as the worst (minimum) value in each day.

For derivation of FiO₂, please see conversion table in [Section 2.5.2](#).

***Analyses of endpoint #4: time to resolution of fever and improvement in oxygenation,
#9: time to improvement in oxygenation, and
#14: time to saturation $\geq 94\%$ on room air***

The analysis of these endpoints will be performed similarly to the primary endpoint.

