Patients who do not experience the event under analysis will be censored at the last observation time point. Patients who die or take rescue medication in the study without experiencing the event will be censored at the earlier date of death or rescue medication started.

***Analyses of endpoint #11: days of hypoxemia,
#12: days with supplemental oxygen use,
#13: days of resting respiratory rate >24 breaths/min, and
#15: ventilator free days in the first 28 days***

The analysis of these endpoints will be performed using the ANCOVA model with treatment group and randomization strata as fixed effects for patients alive by Day 29. The LS treatment mean difference from placebo with standard error, along with corresponding 95 % confidence interval and p-value will be provided. Patient discharged early will be considered as ventilator free until the next hospitalization (if applicable).

Summary statistics with mean, median, standard deviation, minimum and maximum will be provided. Histogram will be provided to illustrate the distribution.

In addition, the percent of days with each endpoint ($100 \times$ number of days with the endpoint divided by number of days of follow up, defined as the earlier date of death or discharge or last

visit up to Day 29) for all patients, will be analyzed using the ANCOVA model with treatment group and randomization strata as fixed effects.

Analyses of endpoint #10: % of patients alive off oxygenation at Day 29, and #16: % of patients with initiation of mechanical ventilation, non-invasive ventilation, or use of high flow nasal cannula, and

These endpoints will be analyzed using a Cochran-Mantel-Haenszel (CMH) test stratified by randomization strata. The difference in proportions of patients for each Sarilumab dose compared to placebo (sarilumab - placebo), along with associated 2-sided 95% confidence levels, and p-value will be provided.

Bar plots will also be provided to illustrate the difference among treatments.

NEWS2

Please find NEWS2 score calculation and details in [Section 2.5.2](#).

Analyses of endpoint #6: Time to change in National Early Warning Score 2 (NEWS2) from baseline, and #7: Time to NEWS2 of <2 and maintained for 24 hours

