The analysis for time to change in NEWS2 from baseline will be performed by evaluating the proportion of patients with clinical risk over time in each category (Low: 0-4; Low-medium: 3 in any individual parameter; Medium: 5-6; High: ≥ 7). The pattern of patients in the categories shifting from baseline and over time will be examined with no formal testing.

The time to NEWS2 < 2 and maintained for 24 hours endpoint will be analyzed similarly to the primary endpoint.

Patients who do not experience endpoint event under analysis will be censored at the last observation time point. Patients who die or take rescue medication in the study without experiencing the event will be censored at the earlier date of death or rescue medication started.

Analyses of endpoint #8: Mean change from baseline to Day 4, 7, 15, 21, 29 in NEWS2

Change from baseline in NEWS2 score at Day 4, 7, 15, 21, and 29 will be analyzed using an ANCOVA model with treatment group and randomization strata as fixed effects, and baseline value as a covariate. The least squares (LS) treatment mean difference from placebo with standard error, along with corresponding 95 % confidence interval and p-value will be provided. Graphical presentations (line plot with mean and error bar) will also be used to examine trends over time using mean values (\pm SE) and mean changes from baseline (\pm SE).

NEWS2 score at each day and their changes from baseline will be summarized for each treatment group through descriptive statistics including mean, median, standard deviation, minimum and maximum.

ICU use, rescue medication, hospitalization and other

Analyses of endpoint #17: % of patients requiring rescue medication during the 28-day period, #18: % of patients with ICU use (among those not in an ICU at baseline)

These endpoints will be analyzed using a CMH method stratified by randomization strata. The difference in proportions of patients for each Sarilumab dose compared to placebo (sarilumab - placebo), along with associated 2-sided 95% confidence levels, and p-value will be provided.

Bar plots will be provided to illustrate the difference among treatments. Summary of immunosuppressive medications used as rescue therapy over time will also be provided.

Analyses of endpoint #19: Days of hospitalization among survivors

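### Secondary time-to-recovery endpoints #3, #4, #7, #9 and #14 censor deaths at the date of death, which can flatter the arm with more deaths or hide its slower recovery

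*SAP*

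**What the plan says.** SAP section 2.4.4.2 sets the rule in three places.

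- **#3 (fever resolution).** Patients who die or start rescue "will not be considered as having an endpoint event and will be censored at the earlier date of death or rescue therapy start date". Living non-resolvers are treated differently: "patients who do not experience resolution of fever will be censored at the end of study".
- **#4, #9 and #14 (fever plus oxygenation, oxygenation, saturation on room air).** Patients who die or take rescue "without experiencing the event will be censored at the earlier date of death or rescue medication started".
- **#7 (NEWS2 below 2 for 24 hours).** The same wording as for #4, #9 and #14.

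All five follow the primary endpoint's method. For #4, #9 and #14: "The analysis of these endpoints will be performed similarly to the primary endpoint". For #7: "The time to NEWS2 < 2 and maintained for 24 hours endpoint will be analyzed similarly to the primary endpoint". The #3 text says the same. SAP Table 3 gives time-to-event endpoints a stratified log-rank test, a stratified Cox model and Kaplan-Meier curves. No cumulative-incidence or competing-risk analysis is planned for them.

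For the primary endpoint, Protocol 9.4.2 says that patients who die or are rescued without earlier improvement "will be censored at the earlier date of Day 29 (for the primary analysis) or rescue medication started". SAP 2.4.4.1 does not repeat a rule for deaths. It does carry the death score of 1 forward to Day 60, which points the same way. Protocol 9.4.3.1 gives no death rule for the other secondary time-to-event endpoints.

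**The concern.** A patient who has died cannot recover. Kaplan-Meier nevertheless treats a patient censored at death as someone who would later have recovered at the rate of those still at risk. Under the #3 rule, a patient who survives with fever stays in the denominator to the end of study, while a patient who dies leaves it. Death therefore counts as less of a failure than survival without recovery, and the documents give no reason for this.

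The protocol describes the population as being at raised risk of death and makes Day 29 survival the key secondary endpoint, so the trial allows for a mortality difference between arms. That is when the rule misleads: the arm with more deaths can appear to recover faster, or its real deficit can disappear. At stake are five hazard ratios, log-rank p-values and Kaplan-Meier curves per dose comparison.

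**Working it through.** **Inputs.** Arm sizes are 160 and 80 (Protocol 9.2) and the test is a two-sided 0.05 log-rank test. The documents give no figure for this rule and no mortality rates. The planned power concerns the primary endpoint and does not bear on the point. Mortality, recovery and timing below are assumptions. The simulations are unstratified and assume no rescue use. HR above 1 means faster recovery on sarilumab unless stated otherwise.

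**Bound by hand.** Kaplan-Meier recovery is 1 − ∏(1 − d/n), with d recoveries among n at risk on each day. Let a proportion R recover and D die unrecovered by Day 29, with no other early censoring.

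- Deaths held to Day 29: n includes the dead, and the estimate is R.
- Deaths censored at death: the estimate lies between R (all deaths after the last recovery) and R/(1 − D) (all deaths before the first recovery).
- With R = 60%, the ceiling is 60/80 = 75% when D = 20% and 60/90 = 66.7% when D = 10%. The ceiling rises with D.

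**Simulation 1.** Recovery days follow gamma(2, 6) and death days gamma(2, 5), capped at Day 28; n = 80 placebo and 160 sarilumab.

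| Deaths, placebo / sarilumab | Recovery, placebo / sarilumab | HR, censored at death | HR, held to Day 29 |
|---|---|---|---|
| 20% / 10% | 60% / 60% | 0.89 | 1.00 |
| 15% / 10% | 60% / 60% | 0.95 | 1.00 |
| 20% / 10% | 60% / 65% | 1.01 | 1.13 |

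In the first row Kaplan-Meier reads 71% on placebo and 65% on sarilumab, within the bounds above, although 60% recover in each arm. Sarilumab is nominally significantly worse in 10% to 11% of trials, against 2.5% if the two arms were equal on the scale tested. In the third row, half of the 10 percentage points saved go on to recover. The HR near 1 then hides a benefit but does not reverse it.

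**Simulation 2, with a different model.** Placebo-like recovery (45% by Day 15, as in Protocol 9.2) in both arms; deaths 20% versus 10%. HRs here are for the arm with more deaths.

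- *Deaths among patients who would not have recovered; true recovery 68.5% in both arms.* Censoring at death gives HR 1.12 and Kaplan-Meier 79.8% versus 73.1%. Holding to Day 29 gives HR 1.00 and 68.6% versus 68.5%. The death-censored HR is 1.06 with 15% versus 10% deaths and 1.20 with 25% versus 10%. With 10% in both arms it is 1.00.
- *Deaths independent of recovery; true recovery 59.0% versus 63.9%.* Censoring at death gives HR 1.00 and Kaplan-Meier 68.3% versus 68.5%, so the deficit vanishes. Holding to Day 29 gives HR 0.90 and 59.0% versus 63.9%.

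**The case against.** **The direction depends on who dies.** A reader might infer that the arm with more deaths must show faster recovery. The documents do not support this. It happens when deaths fall on patients who would not have recovered and few of those saved recover. The first row of the table assumes that none of the 10 points saved recovers by Day 29. If 3 of the 10 recover the HR is 0.96, if 5 recover it is 1.01, and if all recover it is 1.15. This objection stands, and it limits the claim to what the rule can do.

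**The headline mortality gap is large.** It halves mortality. At 15% versus 10%, nominal significance against sarilumab occurs in only about 4% to 5% of trials. This also stands.

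**A death-censored hazard ratio is a legitimate quantity.** It compares recovery rates among patients still alive, and in the first row those rates do differ. The 10% to 11% is an error rate only if the target is equal cumulative recovery. This stands for the hazard ratio. It does not rescue the Kaplan-Meier display, and the SAP does not state which quantity is intended.

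**The stakes are limited and deaths are counted elsewhere.** Day 29 survival is the key secondary endpoint, with an overall-survival curve and hazard ratio. Endpoint #10 requires being alive off oxygen. The SAP also summarizes over time the percentages who died or were on a ventilator, were off oxygen, and were discharged. A reader might infer that the confirmatory error rate is affected. It is not, because the four-step hierarchy in SAP 2.4.4.3 contains only the primary and key secondary endpoints.

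**Conclusion.** The point holds in conditional form. For #3, #4, #7, #9 and #14, death-date censoring departs from the protocol's handling of deaths on the primary endpoint. It makes one minus Kaplan-Meier overstate recovery, and with unequal mortality the overstatement is larger in the arm with more deaths. That arm can then appear to recover faster, or its slower recovery can be hidden.

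Across the assumed gaps of 5 to 15 percentage points in mortality, death-date censoring raised the hazard ratio of the higher-death arm by roughly 5% to 20% relative to the Day 29 rule. With equal mortality the hazard ratio was undisturbed, but both curves were still too high. These sizes rest on assumed mortality, recovery and timing, because the documents give none. The direction of the overstatement does not depend on those choices; whether the apparent effect reverses does. The consequence is confined to nominal p-values, hazard ratios and curves for secondary endpoints. It should be corrected, but it does not threaten the confirmatory tests.

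**What to change.** 1. In each of the three places in SAP 2.4.4.2, replace the death rule with: *Patients who die or take rescue medication without experiencing the event will be censored at the earlier of Day 29 (Day 60 in the final analysis) or the start of rescue medication.* This follows Protocol 9.4.2; the Day 60 clause extends it, since the protocol states only the primary-analysis date. Keeping the earlier-of construction covers a patient who is rescued and then dies. The rescue rule and the separate #3 rule for patients without baseline fever are unchanged.
2. State the same rule in SAP 2.4.4.1, so that a reference to the primary endpoint points to something the SAP itself says.
3. Show recovery as an Aalen-Johansen cumulative incidence curve with death as a competing event. One minus Kaplan-Meier under the new rule need not equal it, because rescue still censors patients early on all five endpoints.
4. The death-censored Cox hazard ratio may stay as a sensitivity analysis, labelled cause-specific.

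The cost is a sentence in each place, a small programming change and one added curve per endpoint, made by the blinded team before database lock. SAP version 2 predates protocol amendment 04 and still describes 2:2:1 randomization, so an update is due anyway. The downside is that the main hazard ratio becomes a subdistribution-type ratio, which is harder to read as a rate among the living. The primary endpoint already has this property under the protocol rule.

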1 OVERVIEW AND INVESTIGATIONAL PLAN

1.1 STUDY DESIGN AND RANDOMIZATION

This study is a randomized, double-blind, placebo-controlled, phase 3 trial to evaluate the efficacy and safety of sarilumab in hospitalized adults with severe or critical COVID-19. The study will be conducted in Europe and other countries except in the United States (US) in up to 100 sites.

Approximately 400 patients will be randomized via interactive response technology (IRT) in a 2:2:1 allocation ratio to sarilumab 400 mg IV, sarilumab 200 mg IV, or placebo. Randomization will be stratified by severity of illness (severe, critical) and use of systemic corticosteroids (yes, no), and balanced by region. All patients will receive a single dose of study drug on Day 1. Patients may receive a second dose with study drug (based on the original treatment group assigned) 24 to 48 hours after the first dose, if they meet prespecified criteria in protocol.

Severity of illness categories:

- Severe disease:
 - Requires supplemental oxygen administration by nasal cannula, simple face mask, or other similar oxygen delivery device
- Critical disease:
 - Requires supplemental oxygen requiring delivered by non-rebreather mask or high flow nasal cannula, or
 - Use of invasive or non-invasive ventilation, or
 - Requiring treatment in an intensive care unit.

Patients will be assessed daily while hospitalized. Patients discharged from the hospital prior to Day 29 will be contacted with a follow-up phone call on Day 29 to assess status and occurrence of re-admission to a hospital. Patients will undergo a series of efficacy, safety and laboratory assessments while in the hospital. Serum IL-6 and other markers will be collected and analyzed in a central laboratory. Nasopharyngeal (NP) samples to monitor viral infection and blood samples may be obtained on Day 1 (pre-dose), 4, 7, 15, 29 (or up until the day of discharge if the patient is discharged from the hospital before Day 29). An individual patient will complete the study approximately 60 days from screening to follow-up on day 60 ± 7 days. Patients will not be required to return to the hospital once discharged.

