Changes from baseline in the 7-point ordinal scale for Day 4, 7, 15, 21, 29 (or until discharge) will be analyzed using an ANCOVA model with treatment group and randomization strata as fixed effects and baseline value as a covariate. The least squares (LS) treatment mean difference from placebo with standard error, along with corresponding 95 % confidence interval and p-value will be provided. Graphical presentations (line plot with mean and error bar) will also be used to examine trends over time using mean values (\pm SE) and mean changes from baseline (\pm SE).

The 7-point ordinal scale at each day and their changes from baseline will also be summarized for each treatment group through descriptive statistics including mean, median, standard deviation, minimum and maximum.

Fever

Body temperature is collected using varying methods (the routes in eCRF are axillary, auricular, oral, rectal) at multiple timepoints each day.

Baseline body temperature is defined as the highest temperature at any time prior to first dose.

Post-baseline body temperature is defined as the highest temperature from each day among all temperatures from different timepoints (morning, evening, etc).

Patients body temperature and its change from baseline will be summarized at each day by treatment group by timepoint over the study period. Graphical presentations (line plot with mean and error bar) will also be used to examine trends over time using mean values (\pm SE) and mean changes from baseline (\pm SE).

All temperatures will be converted to oral values as following:

- Rectal/Auricular subtract 0.6 deg C = Oral deg C
- Axillary add 0.6 deg C = Oral deg C

Analysis of endpoint #3: time to resolution of fever

Resolution of fever is defined as body temperature ($\leq 36.6^{\circ}\text{C}$ [axilla], or $\leq 37.2^{\circ}\text{C}$ [oral], or $\leq 37.8^{\circ}\text{C}$ [rectal or auricular]) for at least 2 consecutive days without antipyretics or until discharge, whichever is sooner.

The analysis will be performed similarly to the primary endpoint.

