Analysis of days of hospitalization among survivors will be performed using the ANCOVA model with treatment group and randomization strata as fixed effects. The LS treatment mean difference from placebo with standard error, along with corresponding 95 % confidence interval and p-value will be provided.

Summary statistics with mean, median, standard deviation, minimum and maximum will be provided. Histogram will be provided to illustrate the distribution.

In addition, the percent of patients died or “on a ventilator”, off oxygenation, and discharged will be summarized by treatment overtime, respectively. The time from first dose to discharge will also be summarized.

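### The SAP's day-count models, labelled ANCOVA, adjust for no baseline measure beyond the two stratification factors, which may cost some precision on secondary endpoints

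*SAP*

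**What the plan says.** SAP 2.4.4.2 gives six count-of-days endpoints the same linear model.

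- Hypoxemia (#11), supplemental oxygen (#12), respiratory rate above 24 (#13) and ventilator-free days (#15): "performed using the ANCOVA model with treatment group and randomization strata as fixed effects for patients alive by Day 29".
- Fever (#5): "The number of days with fever will be analyzed using the ANCOVA model with treatment group and randomization strata as fixed effects".
- Hospitalization (#19): "Analysis of days of hospitalization among survivors will be performed using the ANCOVA model with treatment group and randomization strata as fixed effects".

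For #5, #11, #12, #13 and #15 a further analysis in all patients, using percent of follow-up days, has the same terms. Endpoint #19 has no percent-of-days version. A least-squares mean difference with a 95% interval and p-value is planned for each of the six counts.

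The strata come from SAP 1.1: "Randomization will be stratified by severity of illness (severe, critical) and use of systemic corticosteroids (yes, no), and balanced by region". In contrast, the model for change in the ordinal scale (#2) is an "ANCOVA model with treatment group and randomization strata as fixed effects and baseline value as a covariate", and the model for change in NEWS2 (#8) has the same form.

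**The concern.** An analysis of covariance normally carries a baseline covariate as well as design factors. These six models carry design factors only, so they are stratum-adjusted analyses of variance, and the SAP does not say why nothing more was added.

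The strata are coarse for these outcomes. Under SAP 1.1, the critical category runs from a non-rebreather mask through high-flow cannula and non-invasive ventilation to invasive ventilation, and includes anyone needing intensive care. The SAP's own map from device to ordinal score (SAP 2.4.4.1, used there to fill in missing post-baseline values) places these at 4, 3, 3 and 2. A patient already intubated and one on a mask can share a stratum, although days on oxygen and ventilator-free days depend directly on the support in use at the start. Neither stratum measures temperature or time already spent in hospital.

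At stake is the width of the intervals on secondary endpoints and the ability to correct for chance imbalance inside a stratum. The validity of the comparison is not at stake.

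**Working it through.** **1. The plan's own figure.** No precision or power figure is given for any day count. The only stated figure is at least 90% power for the primary log-rank test with 160 versus 80 patients (SAP 1.3). It reproduces:

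- Exponential hazard ratio from 45% and 70% at Day 15: ln(0.30)/ln(0.55) = 2.014.
- Events by Day 15: 80 × 0.45 + 160 × 0.70 = 148.
- Power at two-sided 0.05: 98.0% (Schoenfeld) or 93.4% (Freedman-type). Longer follow-up gives more.

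This says nothing about the day counts.

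**2. Baseline measures already defined in the SAP.**

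| Measure | SAP section | In the day-count models? |
|---|---|---|
| Severity, corticosteroid use | 1.1 | Yes, as strata |
| Ordinal status, values 2 to 6 | 2.4.4.1 | No |
| Body temperature, highest before dosing | 2.4.4.2 | No |
| SpO2/FiO2 ("ratio is defined as the last available ratio prior to first dose") | 2.4.4.2 | No |
| Hospital stay before dosing | 2.1.1 | No |

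**3. Effect on interval width.** Let ρ be the partial correlation between the day count and the baseline measure, given treatment and strata. Then

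width with covariate / width without = √(1 − ρ²).

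The documents give no ρ, so these values are assumptions:

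| ρ | √(1 − ρ²) | Planned interval wider by |
|---|---|---|
| 0 | 1.000 | 0% |
| 0.1 | 0.995 | 0.5% |
| 0.2 | 0.980 | 2.1% |
| 0.3 | 0.954 | 4.8% |
| 0.4 | 0.917 | 9.1% |
| 0.5 | 0.866 | 15.5% |

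In residual-SD units, the 95% half-width at 160 versus 80 is 1.96 × √(1/160 + 1/80) = 0.268. It becomes 0.256 at ρ = 0.3 and 0.232 at ρ = 0.5. Restricting to Day 29 survivors reduces the numbers but leaves the ratios unchanged.

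**4. What the ordinal score adds once the strata are fitted.** This was simulated with assumed inputs: 240 patients split 160:80; 40% critical; 20% on corticosteroids; score 4 throughout the severe stratum and 2, 3 or 4 (40%, 35%, 25%) in the critical stratum; residual SD 8 days; score entered linearly.

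| Assumed days per scale point | SE with score / SE with strata only |
|---|---|
| 0 | 1.002 |
| 2 | 0.994 |
| 4 | 0.972 |
| 6 | 0.938 |
| 8 | 0.897 |

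The worst case is a 0.2% loss and the best about a 10% lower standard error. The last row corresponds to ρ = √(1 − 0.897²) = 0.44. All of the gain arises in the critical stratum, because the score is constant in the severe one.

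**5. Room for chance imbalance.** Assume 40% critical and 30% of those ventilated. There are then 64 and 32 critical patients, and the between-arm difference in ventilated share has SD √(0.3 × 0.7 × (1/64 + 1/32)) = 0.099, about 10 percentage points. The planned models cannot adjust for it.

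**The case against.** A reader might infer that these models have no baseline adjustment at all. The documents do not support that. Severity and corticosteroid use are baseline variables and are in every model. Severity is defined largely by oxygen device, so the ordinal score overlaps with a term already fitted. In the severe stratum the score should be almost constant at 4.

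A reader might also infer that the SAP contradicts itself, because #2 and #8 carry a baseline value. It does not. Those are change scores with a baseline of their own. A count of days after dosing has none, so a related measure must be chosen for each endpoint. The SAP's division between the two types of outcome is coherent.

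Three further points stand. Chance imbalance is sampling error that the planned interval already reflects. Multiplicity control covers only the primary and key secondary endpoints (SAP 2.4.4.3), and Protocol 9.4.3.1 asks only for descriptive summaries of durations. The added terms also need some care: a factor running from 2 to 6 may have sparse levels, and for #19 the SAP does not say whether days count from admission or from dosing.

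These points limit the size and importance of the issue. They do not remove it: the critical stratum is mixed with respect to starting support, and neither stratum captures temperature or prior stay. For time to fever resolution (#3), the SAP itself treats baseline fever as decisive by censoring patients without it at first dose, yet the fever-days model leaves it out.

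**Conclusion.** The point holds as an optional gain in precision. Six day-count models and the five matching percent-of-days models use no baseline measure beyond the strata, and the label ANCOVA is loose for them.

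The planned intervals are between 0% and about 15% wider than necessary for ρ from 0 to 0.5, and the true value could be close to zero. That range is an assumption, since the documents supply no SD or correlation, and nothing in them suggests that one value of ρ fits all six outcomes.

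Two stronger readings should be set aside. The first is that the estimates are biased or invalid: omitting a prognostic covariate from a randomized comparison does not do that. The restriction to Day 29 survivors is a separate question, which a baseline covariate would not settle. The second is a definite, large loss. For example, if baseline explained 30% of within-stratum variance, adjustment would be worth 1/(1 − 0.30) = 1.43, or 43% more patients, but the documents give no basis for that 30%.

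**What to change.** Before unblinding for the primary analysis, the study team without access to the interim results could amend SAP 2.4.4.2 as follows, keeping the strata in every model:

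- #11, #12, #13 and #15, counts and percent of days: add baseline ordinal status as a factor with sparse levels collapsed, for example 2, 3 and 4 or above.
- #5, count and percent of days: add baseline temperature, converted to oral by the SAP's own rule.
- #19: add days in hospital before dosing, and state whether the outcome counts from admission or from dosing. The range of this covariate is limited, because Protocol 5.1 admits patients with at most 7 days in hospital.

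The SAP should also say how a missing baseline value is handled. If the sponsor prefers the present models, it is enough to drop the label ANCOVA and give the reason.

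The cost is a few sentences of SAP text and minor programming, with no new data. If the covariates turn out not to be prognostic, the loss is negligible (0.2% in the simulation for the ordinal score).
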